7.1 Data Management

All data collected for analysis will be de-identified and assigned a unique study number. Any data collected on paper forms will be kept in a locked file cabinet at HRC. Data collected on paper forms will be entered and stored on a password-protected secure server at HRC. When possible, data will be collected directly via our electronic data capture system (e.g., REDCap).

The Marcus Institute for Aging Research primarily employs the REDCap system to facilitate data management operations. REDCap is a full-featured clinical trials data management system (DMS) accessible to data entry and data analysis workstations using secure Web technologies. The REDCap product is developed and maintained by Vanderbilt University in cooperation with REDCap Consortium members, including HRC. HSL hosts and maintains a dedicated instance of REDCap for use across our research enterprise. Each research study is provided separate project workspace in which all of the study data are stored in a MySQL relational database on the private corporate network behind several firewalls and located physically within the HSL data center.

7.2 Participant Tracking

Each recruited participant will be tracked closely throughout study enrollment. If desired, a study events calendar will be created for each participant. Any outstanding or incomplete visits will be accessible in real time to the study team. The study team will maintain regular communications with each study participant throughout enrollment, through regularly scheduled follow up calls, and established retention strategies will be used as discussed in §4.7.

CHAPTER 8 DATA SAFETY MONITORING PLAN

8.1 Participant Risks

Participation in this study may be associated with minor risks or safety concerns. The potential risks of this study fall into 5 categories: 1) those related to research participation; 2) those related to testing procedures; 3) those related to the intervention or placebo products; 4) those related to sleep; and 5) those related to optional study assessments. The risks are outlined for each category below:

Minor Risk of Participation in Research: With any study, risk of breach of confidentiality is possible since we are collecting personal health information.

Minor Risk of Testing Procedures: The potential risks of the testing procedures are minor since the majority will be questionnaire based assessments. It is possible that participants may find the questionnaires tedious or may be uncomfortable being asked about sensitive topics like suicidality. The participants are also asked to wear a sensor to objectively measure physiological data. This device may cause slight discomfort or potential rash and be tedious to maintain charged and/or continuously wear. The participants may also experience pain or bruising that results from the blood draw. With any puncture of the skin, there is an increased likelihood for infection, although this is minor. It is also possible that since we are asking participants to consume liquids closer to bed-time, that it might cause frequent urinations during the night.

Minor Risk Related to Intervention or Control Products: We do not anticipate any major risks for the participants with consumption of either the intervention or placebo products. Participants might grow weary and uninterested in consuming the products each day over the 4-week periods.

Minor Risk Related to Sleep: Individuals are eligible for this study because they have reported difficulty sleeping. Individuals with sleep problems are more likely to have increased pain, stress, and depressive symptoms during our study.

Minor Risk Related to Optional Study Assessments: It may be tedious and inconvenient to collect a 24 hour urine sample. It may also be unpleasant to collect fecal samples for the study.

8.2 Risk Minimization

We will attempt to minimize the identified risks as specified below:

Risk Minimization of Participation in Research: To minimize the risk of breach in confidentiality, all primary study data will be recorded with computer tablets on electronic case report forms (CRF) or as digital files generated from laboratory equipment. All data recording will be in accordance with procedures and guidelines outlined in the study's Manual of Procedures (MOP) authored by the study team. Participant confidentiality will be maintained by recording subject data using a unique subject identifier. Identifiable data, such as contact information and medical record numbers, will be recorded and stored separately from the clinical study data. Any paper-based study material and any identifiable data will be kept separate in a locked file cabinet accessible by authorized study staff only. Only the study staff directly responsible for the data collection and the safety of the participant will have access to identifiable information. All electronic CRF data will be stored securely in an electronic data capture

and management system. Raw electronic instrumentation data will be organized and saved on a private network file dedicated to the research project. Only those listed on the approved IRB protocol will have access to subject data. Subject data will be coded and locked in a file cabinet in a locked office. Identifying information will not be used during discussion, presentation or research publication. All documents and electronic data will be archived for a minimum of three years, or as required by the IRB and federal regulations, after the completion of the clinical trial. The study will be registered at clinicaltrials.gov.

The Hinda and Arthur Marcus Institute for Aging Research employs the Research Electronic Data Capture (REDCap) system for data capture and data management operations. REDCap is a full-featured clinical trials data management system (DMS) accessible to data entry and data analysis workstations using secure Web technologies. While REDCap can be used to collect virtually any type of data (including 21 CFR Part 11, FISMA, and HIPAA-compliant environments), it is specifically geared to support online or offline data capture for research studies and operations. REDCap is developed and maintained by Vanderbilt University in cooperation with REDCap Consortium members, including HRC. HSL hosts and maintains a dedicated instance of REDCap for use across our research enterprise. Each research project is provided separate workspace in which all of the study data are stored in a MySQL relational database on the private corporate network behind several firewalls and located physically within the HSL data center.

Risk Minimization of Testing Procedures: The majority of the testing procedures will be questionnaire based and/or passively obtained via wearable devices. Participants will be advised that they can refuse to answer any of the questions. Participants will be permitted to rest between studies to prevent fatigue. To minimize the risk of being uncomfortable during questionnaires on sensitive topics like suicidality, only trained research staff will administer the questionnaires. Research staff will be trained to administer them in a calm, welcoming demeanor and will reassure the participants that the assessment(s) can stop at any time.

To minimize risk associated with the sensor, individuals will be provided detailed instruction on how to maintain and wear the sensor.

To avoid any risk associated with blood draws, only individuals with trained phlebotomist skills will draw blood using standard, sterile safety procedures to minimize risk of infection. Unless performed at the participant's home/residence or other HSL housing facility, blood draws will be done at our study clinic that resides in the Hebrew Rehabilitation Center, which is a functioning hospital. Thus, in the rare case a participant needs additional care that the study team is not qualified to provide, the individual will be transferred immediately to the adjacent hospital.

To minimize any risk associated with fluid intake close to bed time, participants will be called within 5 days of starting their intervention arm to check in to see if nocturia is occurring. If the participant reports that they are urinating in the night more than usual which is disturbing their sleep, then the study staff will work with the participant to modify their consumption schedule to avoid the sleep disturbance.

Risk Minimization of Intervention Product: Individuals with allergies to intervention products will not be included in this study to avoid any adverse effects/allergic reactions. We anticipate that the intervention products will be well-tolerated by participants since they consist of dietary products that are regularly consumed. Regardless, we will ask participants about any complaints or adverse events that are directly related to the study intervention products. We plan to track diarrhea, gas, bloating, abdominal pain, constipation etc. If a participant develops a health problem or a potential health problem (in addition to the ones outlined below), the PI will be notified ASAP to help decide whether the participant should continue in the study, and/or what further steps regarding medical evaluation should be performed.

Risk Minimization of Sleep: We will proactively assess pain, stress, and depressive symptoms. These scores will be regularly reviewed by the PI of the study. If any of the scores concern the PI for the participant's safety or the participant informs study staff that symptoms have become more severe than usual, they will contact the study participant and may contact their physician, providing the participant has given consent to do so. Additionally, suicidal ideation will also be monitored at visits while the participant is on the intervention products to identify individuals who may need psychiatric care outside this study. If the participant is deemed to be dangerous or at imminent risk of harm, study staff will contact emergency services (i.e., #911) for immediate medical assistance.

Risk Minimization of Optional Study Assessments: To minimize risk associated with collecting 24-hour urine sample, individuals will be provided detailed instruction on how to collect the urine sample. They will also be reminded a few days prior of when to collect their urine. All materials for urine collection will be provided to that participants. To avoid any unpleasant experience collected a fecal sample, study staff will provide detailed instruction on how to collect the sample. Furthermore, to avoid the burden of storing it in the participants freezer, study staff will pick up the collected samples as soon as possible from the study participant.

General Risk Minimization: The proposed protocol requires up to 7 visits over a total 12 weeks and therefore imposes a moderate amount of participant burden with respect to time and effort. Our institute has a strong track record of successful clinical research requiring similar participation, and retention has been high in these projects. The Clinical Research Laboratory at the Marcus Institute is located near a cafeteria and rest room, and is equipped with comfortable seating. TV or movies can be accessed via the internet to keep individuals occupied during rest periods. Several additional strategies will be employed to minimize participant burden and maximize adherence to the protocol. We will:

- Develop a personal relationship between participants and members of the staff.
- Schedule appointments at convenient times with familiar staff.
- Explain to participants all aspects of their participation and follow up. We will demonstrate and practice study procedures before beginning data collection.
- Provide reminders of all appointments and follow-up phone calls.
- Include personal notes in the participant's data file to remember events in the life of the participant; these can be commented on at the next visit (e.g., birthday, birth of a grandchild).
- Provide snacks during all visits.
- Provide transportation for all visits, if required.
- Provide free on-site parking.
- Compensate participants for visits.

8.3 Quality Assurance and Safety Monitoring

The PI will assume primary responsible for ensuring participants' safety on a daily basis. Since this is a single-site, phase 1/2 pilot study, without high risk, our study will not require an official Data and Safety Monitoring Board (DSMB).

8.4 Adverse Event Collection and Reporting

Any adverse event (AE) or serious adverse event (SAE) will be logged using forms either provided by or modeled after the forms that are provided by the NIA Clinical Research Toolbox .

Adverse Event Definition and Categorization

An AE is any untoward medical occurrence in a participant, whether or not it is causally related to the study. An AE can therefore be any unfavorable and unintended sign (including an abnormal laboratory finding, for example), symptom or disease temporally associated with the study. We have defined specified thresholds of change in some of our assessments (e.g., change in related symptom severity) that will qualify as an AE, which is outlined in our manual of procedures. All adverse events will be recorded on the appropriate case report forms, source documents and logs. The PI and/or trained staff member will evaluate all adverse events as to their severity and relation to the intervention. The severity of AEs will be graded as follows:

Mild: Awareness of a sign or symptom but easily tolerated.

Moderate: Discomfort sufficient to cause interference with usual activity or to affect clinical status.

Severe: Incapacitating with inability to do usual activity or to significantly affect clinical status.

Life Threatening: The participant was at immediate risk of death from the adverse event as it occurred.

The PI will also assess the relationship of any AE to the study, based upon available information, using the following guidelines:

0 = Unlikely: No temporal association, or the cause of the event has been identified

1 = Possible: Temporal association, but other etiologies are likely to be the cause; however, involvement of the study procedures cannot be excluded.

2 = Probable: Temporal association, other etiologies are possible, but not likely.

To determine the attribution and temporal association of an adverse event we will consider the following:

1) Whether the participant reports they have experienced the same symptom prior to the study intervention.

2) Whether the symptom occurred and resolved within 24 hours of taking the study intervention.

The PI and/or study staff will consider the symptom according to the conditions stated above and determine temporality.

Definition of a Serious Adverse Event

A serious adverse event (SAE) is any experience that results in any of the following outcomes:

- Death
- Is life-threatening
- Inpatient hospitalization or prolongation of hospitalization

A persistent or significant disability/incapacity. Important medical events that may not result in death, be life-threatening, or require hospitalization may be considered a serious adverse event when, based upon appropriate medical judgment, they may jeopardize the patient or participant and may require medical or surgical intervention to prevent one of the outcomes listed in this definition. We do not anticipate any Serious Adverse Events with our intervention.

Adverse and Serious Adverse Event Reporting

There is a potential for adverse events and incidental findings during this study. A structured questionnaire asking about adverse events will be assessed during each visit of the intervention period. However, when any adverse has been identified, the study team will take appropriate action necessary to protect the study subject and then complete the Adverse Event form that will be modeled after the form provided by the NIA Clinical Research Toolbox. This form requires Principal Investigator review and signature. After review by the Principal Investigator any adverse event will be reported to the IRB as appropriate.

AE's that 1) are unexpected in nature, severity, or frequency, 2) are possibly, probably, or definitely related, and 3) suggests that the research places participants at a greater risk of harm than previously known or recognized, will be reported to the IRB within 2 weeks of the event.

If a serious event occurs, it will be brought immediately to the attention of the Principal Investigator to decide if immediate treatment is necessary, initiate such treatment in an appropriate hospital or urgent care setting, contact the primary care physician if the participant provides consent to do so, and notify the IRB. A Serious Adverse Event form that is modeled after the one provided by the NIA Clinical Research Toolbox will be completed, which requires Principal Investigator review and signature. If an AE is defined as a SAE, the Principal Investigator will be notified as soon as the event is known about. Routine reporting of expected SAEs will be monthly or quarterly as appropriate. If the SAE is unexpected or unanticipated, the Principal Investigator will notify the IRB within 48 hours of being notified.

Unanticipated problems or adverse events will be reported according to the IRB's written guidelines for interventional studies. Unanticipated problems and serious adverse events that are probably, possibly, or definitely related to the study will be reported as soon as possible from the time of learning of the event, but

reported within 10 days to the IRB per written IRB guidelines. The IRB will be provided a written report submitted and a submission of the incident via the eIRB system. This form will record any adverse symptoms and/or study protocol deviations. Study staff will reference a Subject Safety Event Reporting Decision Chart provided and regularly updated by the IRB to determine whether an event needs to be reported to the Advarra IRB.

All other adverse events/study incidents will be logged on an Adverse Event log and reported to the IRB following the appropriate reporting times as defined by the IRB.

For less serious or incidental findings the Principal Investigator will speak with the participant about the finding. If necessary, the PI may suggest appropriate follow-up with the participant's primary care and/or provide a letter describing the findings and need for follow-up.

Any adverse events that take place during testing will be reported to the PI and recorded in the database. The PI will have ultimate responsibility for monitoring participant safety in the trial. The investigators will be responsible for reviewing each adverse event in a timely fashion, and reporting all incidents to the appropriate regulatory agencies according to written guidelines.

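### Section 8.4 codes an adverse event Unlikely once its cause is identified, without excluding study causes, and its scale has no exact level for an established study cause

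*Combined protocol and SAP*

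**What the plan says.** Section 8.4 introduces the relatedness scale as follows: "The PI will also assess the relationship of any AE to the study, based upon available information, using the following guidelines". The scale then has three codes:

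- The lowest code, met if either of its two conditions holds, is "0 = Unlikely: No temporal association, or the cause of the event has been identified".
- The middle code, which sets the study against competing explanations, reads "1 = Possible: Temporal association, but other etiologies are likely to be the cause; however, involvement of the study procedures cannot be excluded".
- The highest code, for events where a competing explanation is weak, reads "2 = Probable: Temporal association, other etiologies are possible, but not likely".

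There is no fourth level. Later in 8.4, two IRB reporting rules depend on relatedness. The 2-week report covers events that are unexpected, that "are possibly, probably, or definitely related", and that point to a greater risk than was previously recognised. The 10-day report covers "Unanticipated problems and serious adverse events that are probably, possibly, or definitely related to the study".

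Section 8.1 names procedure-related risks in advance, among them "The participants may also experience pain or bruising that results from the blood draw" and, for the watch, "This device may cause slight discomfort or potential rash and be tedious to maintain charged and/or continuously wear".

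**The concern.** Code 0 applies if either of two conditions is met, and the second is simply that the cause is known. The text does not say that the cause must lie outside the study. Taken at its word, the scale gives its lowest relatedness score to the events whose link to the study is most certain.

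The top of the scale has a related fault. Code 2 describes events for which another explanation exists but is not likely. An event for which no other explanation exists is not described anywhere, yet the reporting rules assume that a definite category is available.

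What is at stake is safety classification. Relatedness is one condition of two IRB reporting routes, and under 8.3 the study has no formal data and safety monitoring board that might notice a misclassified event.

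**Working it through.** No arithmetic applies. The check is to run the literal code definitions over the possible cases and then see which reporting rules use the result.

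**Step 1. Which codes fit?** All rows assume a temporal association. The third column takes code 0 as printed. The fourth takes it as meaning a non-study cause, with codes 1 and 2 unchanged.

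| Identified cause | Other etiologies | Codes met, as printed | Codes met, code 0 read as non-study cause |
|---|---|---|---|
| Study product or procedure | None possible | 0 only | None |
| Study product or procedure | Possible, not likely | 0 and 2 | 2 only |
| Something else | Likely | 0, and 1 if study involvement cannot be excluded | Same |

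The first row is the defect. As printed, the only match is the lowest code. On the contextual reading the event leaves code 0, but code 1 fails because no other etiology is likely, and code 2 fails strictly because no other etiology is possible. The second row is ambiguous as printed and resolves on the contextual reading. The overlap in the third row is the same on either reading and does not involve study-caused events.

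**Step 2. Do the other attribution aids in 8.4 settle it?** Two considerations are listed: whether the participant had the same symptom before the intervention, and whether the symptom arose and resolved within 24 hours of taking the product. Neither says what kind of cause code 0 refers to, and the second does not address events caused by a procedure such as the blood draw.

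**Step 3. Do the reporting terms match the scale?** The scale yields Unlikely, Possible or Probable. The 2-week and 10-day rules use possible, probable and definite. The definite category cannot be produced by the scale.

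**Step 4. Which rules could a wrong code 0 affect?**

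| Rule | Relatedness condition? |
|---|---|
| Logging of all adverse events (8.4) | No |
| 48-hour IRB notice of unexpected SAEs (8.4) | No |
| IRB decision chart (8.4) | Not tied to the code in the documents |
| 2-week IRB report (8.4) | Yes, with two further conditions |
| 10-day IRB report (8.4) | Yes |
| Five feasibility endpoints (5.4): recruitment, attrition, dose compliance, data capture, practicality | No |
| Statistical analyses in Chapter 6 | No tabulation of related events is planned |

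The exposed case on the 2-week route is an unexpected, non-serious event that raises the known risk and has an established study cause. Coded 0, it would fail the relatedness condition. On the 10-day route the code bears on the relatedness condition, although an unexpected SAE still goes to the IRB within 48 hours.

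**The case against.** The best answer is that context makes the meaning clear. The scale measures relationship to the study, so recording an event known to be caused by the juice as Unlikely would contradict itself. Codes 1 and 2 both set the study against other etiologies. Section 8.5 provides for SAEs thought to result directly from the products or procedures, so the protocol expects such events to be recognised. The codes are guidelines for the PI and not an algorithm. This stands as far as intent goes: the authors evidently meant a non-study cause. It does not supply a code for the first row of the table, and it does not reconcile the scale with the reporting terms. Section 8.4 also lets a trained staff member evaluate relation to the intervention, so the printed wording should be clear without the PI's knowledge of the intent.

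Three stronger readings are tempting, and the documents do not support them.

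- *Study-caused events will be scored as unrelated.* The label is Unlikely, no code says unrelated, and the text only permits this coding.
- *Such events will be kept from the IRB.* They are still logged, unexpected SAEs are notified whatever the code, other events are reported on the IRB's own timelines, and staff consult the IRB's decision chart. Bruising and watch rash illustrate the coding problem, but as foreseen risks they would ordinarily fail the unexpectedness condition of the 2-week report anyway.
- *The feasibility conclusion or a harms table is biased.* No feasibility endpoint uses relatedness, and Chapter 6 plans no table of related events.

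**Conclusion.** Wrong as written, low severity. Followed literally, code 0 misclassifies an event with an established study cause. Read as intended, the scale still lacks an exact code for that event and lacks the definite level that two reporting rules use.

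The reach is two IRB reporting routes, the 2-week and the 10-day. The matter is one of safety classification and reporting; the efficacy and feasibility analyses are untouched. The documents give no adverse event frequencies, so the number of events affected cannot be estimated and none is claimed.

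The conclusion rests on the printed definitions in 8.4 and on the assumption that the Manual of Procedures and the adverse event form, which are not in the documents, do not already carry corrected wording.

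**What to change.** In section 8.4:

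1. Restrict the second limb of code 0 to read *a cause other than the study products or study procedures has been identified*.
2. Give events with no other etiology a place at the top of the scale, in one of two ways. Either add *3 = Definite*, which matches the terms already used in the reporting rules, or widen code 2 to *other etiologies are absent or not likely* and remove the definite category from the 2-week and 10-day rules.
3. Carry the same wording to the adverse event form.

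In the table above, the first row then maps to the new code 3 or to the widened code 2, and the second row maps to code 2 alone.

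The cost is a few sentences in the protocol and the form, with no added visits, staff or participants. The one consequence is that a few more events may be classed as related.

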Eligible participants will be asked to avoid consumption of tart cherry products, as well as supplemental forms of flavonoids, magnesium, and tryptophan for the entire study in order to isolate the effects of our intervention on the proposed outcomes. They will also be advised to avoid intake of foods, beverages, and medicines that may impact sleep (e.g., alcohol, caffeine, sleep aids, medications that induce drowsiness). Participants will undergo a 1-week (approximately 7 nights) pre-intervention assessment of sleep quantity via a digital wearable device that measures aspects like sleep quantity and physical activity (e.g., Garmin Watch™), which will serve as the baseline assessment for these measures. Furthermore, participants will be asked to record the time they went to bed and the time they got out of bed (i.e., sleep diary) for the entire study. Participants will also be asked to complete a 3-day diet record. At the baseline visit, medical history, and basic anthropometric information will be collected. Participants will provide a urine sample and fasted blood samples for biomarker analyses, complete questionnaires (e.g., sleep quality, mood, etc.) and have their vitals measured. Blood samples will be collected between 8-10 am, to avoid the impact of time of day on markers. After randomization to one of the intervention arms, participants will be asked to consume their intervention product twice per day for approximately 4 weeks, while also wearing the digital sleep sensor. Half of the intervention dose is intended to be consumed at approximately 5 pm and the other approximately 1 hour before bedtime. Individuals may receive reminder messages via their digital wearable device or via email/text to remind them about their study responsibilities (e.g., charging their devices etc). All assessments that were performed at baseline will be repeated approximately 4 weeks later at follow-up (e.g., urine sample, blood draw, questionnaires). After approximately 2 weeks of a washout period (to reduce the impact of a carry-over effect from the intervention), participants will complete the same schedule with the other intervention product.

Telephone Pre-screen (~30 minutes): Volunteers will be asked about demographic information, sleep behaviors/insomnia, medication/supplement use, any past/present medical conditions and/or treatments, as well as other exclusionary criteria.

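### Section 8.4 asks whether a symptom cleared within 24 hours, so a symptom sustained by nightly intake tends to be steered towards a rating of Unlikely

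*Combined protocol and SAP*

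**What the plan says.** Section 8.4 rates the relation of an adverse event to the study on three levels. The lowest is "0 = Unlikely: No temporal association, or the cause of the event has been identified". The two higher levels, Possible and Probable, both start from a temporal association and differ in how likely other causes are.

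To judge attribution and timing, the section gives two considerations:

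- "Whether the participant reports they have experienced the same symptom prior to the study intervention"
- "Whether the symptom occurred and resolved within 24 hours of taking the study intervention"

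It then states: "The PI and/or study staff will consider the symptom according to the conditions stated above and determine temporality".

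On exposure, Section 5.2 says that "participants will be asked to consume their intervention product twice per day for approximately 4 weeks", and adds: "Half of the intervention dose is intended to be consumed at approximately 5 pm and the other approximately 1 hour before bedtime". On the symptoms of interest, Section 8.2 says: "We plan to track diarrhea, gas, bloating, abdominal pain, constipation etc".

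The rating feeds into reporting. The two-week report to the IRB in Section 8.4 has three joint conditions, one of which is that the events "are possibly, probably, or definitely related". The same section sets a 10-day limit for unanticipated problems and serious events that are at least possibly related.

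**The concern.** Asking for resolution within a day suits a single exposure: if a symptom appears after one dose and then clears, that pattern supports a link. Under repeated daily exposure the reasoning turns round. A symptom that the product causes can be expected to last, or to be renewed, for as long as intake continues. Persistence then says nothing against a link, yet the consideration counts it that way.

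At stake is the record of product-related events in a pilot whose purpose is to inform a later trial. If persistent symptoms are under-attributed, the products look better tolerated than they are. The study has no data and safety monitoring board (Section 8.3) and leaves the rating to the principal investigator and staff, so the written guidance carries more weight than it otherwise would.

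**Working it through.** The plan states no figure on this point, so the check is clock arithmetic followed by a reading of the rule.

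**Inputs**

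- First dose: about 5 pm (Section 5.2).
- Second dose: about 1 hour before bedtime (Section 5.2).
- Usual bedtime: 8 pm to 1 am (Section 3.3), so the second dose falls between about 7 pm and midnight.
- Duration: about 4 weeks per period, taken as 28 days.

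**Step 1: exposure.** 2 doses × 28 days = 56 doses per period.

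**Step 2: longest gap between doses.**

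| Bedtime | Second dose | Evening gap | Gap to next 5 pm dose |
|---|---|---|---|
| 8 pm | 7 pm | 2 h | 24 − 2 = 22 h |
| 1 am | midnight | 7 h | 24 − 7 = 17 h |

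The longest gap is 17 to 22 hours. Sections 5.2 and 8.2 allow the timing to be modified, but two separate daily doses at fixed times always leave gaps below 24 hours.

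**Step 3: the onset part.** A compliant participant is never more than about 22 hours past a dose, so almost any symptom that starts during intake meets the onset part. It separates nothing.

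**Step 4: the resolution part.** If a symptom starts L hours after the latest dose, it must clear within 24 − L hours to meet the condition for that dose. With L between 0 and 22, the time allowed runs from 24 hours down to 2. A symptom that lasts longer fails, whatever its cause.

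**Step 5: other readings of the clock.** If onset and resolution are both timed from the same dose, restarting the clock at each dose does not help: a continuous symptom still fails. If resolution may instead be timed from any later dose, almost every symptom that ends during intake passes, and the consideration no longer sorts anything. Neither reading gives a useful test.

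**Step 6: from the consideration to the rating.** The text does not spell out how each answer affects the rating, but a negative answer can only sensibly count against a temporal association. Without that association both Possible and Probable are closed, which leaves Unlikely. The first consideration, about earlier experience of the symptom, does not deal with duration. Nothing else in the document says how to rate a symptom that begins after intake and persists while intake continues.

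**Step 7: measurement.** Symptoms are scheduled for assessment at Weeks 1, 3, 5, 8, 10 and 12 (Section 5.2). Whether a symptom cleared within a day of a particular dose may therefore rest on recall.

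**The case against.** The strongest reply is that this is guidance and not a pass/fail rule. Section 8.4 presents the two items as matters to consider, and the principal investigator rates on the information available. A new symptom would favour a link on the first item even if it persisted. That stands. A reader might infer that every persistent symptom is automatically rated unrelated. The documents do not support this: they give no such mapping, and the lowest label is Unlikely.

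A reader might also infer that persistent gastrointestinal complaints would be lost from IRB reporting. For the two-week report that goes too far. Relatedness is only one of its three conditions; the event must also be unexpected and suggest greater risk than was known. Foreseen symptoms fall outside it however they are rated. The 10-day report of related serious events does depend on relatedness.

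Nor can an effect on the discontinuation rule in Section 8.5 be shown. That rule speaks of serious events thought to be directly related and does not refer to the rating scale.

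Several safeguards do not depend on the rating. All adverse events are recorded, each form needs the principal investigator's review, unexpected serious events go to the IRB within 48 hours, and severe events prompt a decision on continuation. Symptoms on both blinded products can also be described without any attribution. These points limit the consequence but leave the wording unsuited to daily intake.

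Finally, the documents do not say how often symptoms outlast a day. Gas or bloating that comes and goes after each evening's intake would meet the condition. The manual of procedures was not available, but Section 8.4 cites it only for the thresholds at which a change counts as an adverse event.

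**Conclusion.** The point holds as a tendency. With gaps of at most about 22 hours between doses, the onset part of the second consideration is met by nearly every symptom during intake, so resolution does the sorting, and it counts persistence under continued exposure against a link. The direction is towards under-attribution, which makes the products look better tolerated in the recorded ratings. It could affect the 10-day report of related serious events and, for unexpected events only, the two-week report.

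The number of events affected cannot be estimated from the documents. The conclusion assumes compliance with two doses each evening and that some product-related symptoms last beyond a day. Chapter 6 plans no analysis that uses relatedness, so the efficacy tests are unaffected. This is a modest wording fault that is cheap to correct.

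**What to change.** In Section 8.4, delete the words *and resolved*. That alone would leave a condition that almost every symptom meets, so also base temporality on onset or worsening after the product was started in that period, compared with the symptom assessment before product at Week 1 or Week 8. Both assessments are already scheduled.

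Record resolution as a separate item on the event form. For symptoms arising in period 1, note whether they had stopped by Week 8 and whether they recurred in period 2. These checks are not available for period 2: no symptom assessment follows Week 12, and a symptom that first arises in period 2 cannot be checked for recurrence on the other product. No visits need be added.

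The cost is a change of wording in Section 8.4 and on the form. The downside is that more events, possibly many more, will be rated at least Possible. The likelihood of other causes would then separate Possible from Probable, as the scale already provides.
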